9.2. Sample size considerations

A **maximum of 2,000** subjects will be enrolled for a 2-year follow-up period. Assuming a drop-out rate of 10% the first year and a drop-out rate of 20% the second year, the final analysis will be done on approximately **3300** person-years overall.

In order to evaluate the precision with a sample size of **3,000** subjects, the 95% confidence interval (CI) (Poisson exact distribution and normal approximation of the Poisson distribution accounting for a design effect) for a range of expected incidences rates of AFI due to LCD were computed. The 95% CI for a range of expected incidences rates for DENV specific LCD were also presented (see [Table 17](#)).

(Amended 01 March 2017)

Estimating design effect and precision

The normal approximation of the Poisson distribution was used for calculating 95% CI for this cluster design. The variance was adjusted for a design effect of 2.6 to account for the between-cluster variability. The design effect measures the increase in the standard error of the estimate due to the sampling design used and is given by: $D = 1 + (b - 1) \rho$, where ρ is the rate of homogeneity (a measure of variability and equivalent to the “intra-cluster correlation”) and b is the average number of subjects sampled per household. Here we assumed b to be 5. Although, in theory ρ can have a value up to 1, in practice values higher than 0.4 are uncommon [Bennett, 1991]. We used a conservative estimate of 0.4 for this study. The design effect is then estimated to 2.6.

Table 17 95% CI with design effect of 2.6

	Number of cases	Number of person-years	Incidence of LCD (per 100 person-years)	95% CI Poisson exact		95% CI Normal approx with design effect of 2.6	
				LL	UL	LL	UL
Overall	10	3300	0.30	[0.15 ; 0.56]		[0.00 ; 0.61]	
	20	3300	0.61	[0.37 ; 0.94]		[0.18 ; 1.03]	
	30	3300	0.91	[0.61 ; 1.30]		[0.38 ; 1.43]	
	40	3300	1.21	[0.87 ; 1.65]		[0.61 ; 1.82]	
	50	3300	1.52	[1.12 ; 2.00]		[0.84 ; 2.19]	
	60	3300	1.82	[1.39 ; 2.34]		[1.08 ; 2.56]	
DENV specific	4	3300	0.12	[0.03 ; 0.31]		[0.00 ; 0.31]	
	8	3300	0.24	[0.10 ; 0.48]		[0.00 ; 0.51]	
	12	3300	0.36	[0.19 ; 0.64]		[0.03 ; 0.70]	
	16	3300	0.48	[0.28 ; 0.79]		[0.10 ; 0.87]	

(Amended 01 March 2017)

CI: confidence interval**DENV:** dengue virus**LCD:** laboratory Confirmed Dengue**LL:** lower limit;**UL:** upper limit

At time of analysis, the design effect of this study will be estimated using the following formula [Bennett, 1991]:

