$$DE = \frac{s^2_{\text{CLUSTER SAMPLE}}}{s^2_{\text{SIMPLE RANDOM SAMPLE}}}$$

With

$$s^2_{\text{CLUSTER SAMPLE}} = (c/\sum x_i)^2 (\sum y_i^2 - 2p \sum x_i y_i + p^2 \sum x_i^2) / [c(c-1)]$$

$$s^2_{\text{SIMPLE RANDOM SAMPLE}} = p(1-p)/n$$

Where, c is the number of clusters, x_i and y_i are the number of person-years and the number of cases, respectively in the i^{th} cluster, n is the total number of person-years and p is the overall proportion $\sum y_i / \sum x_i$.

The intra-cluster correlation ρ may then be estimated as:

$$\rho = (DE - 1) / [(\sum x_i/c) - 1]$$

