9.6. Analysis of primary and secondary objectives

The following analyses will be performed:

- Computation of incidence rate of AFI due to LCD and due to non-LCD with 95% CI: the numerator will be the number of subjects with AFI due to LCD and due to non-LCD during the study period. The denominator will be the total person-years at risk.
- Description of signs and symptoms of AFI due to LCD and due to non-LCD will include the percentage of AFI presenting each sign or symptom (any intensity and grade 3) during the 7-day period from the onset of fever (body temperature $\geq 38^{\circ}\text{C}/\geq 100.4^{\circ}\text{F}$). Duration of signs and symptoms will also be described for LCD and non-LCD episodes. Analysis will be done overall and then separately for episodes of AFI occurring in subjects < 5 years of age, in subjects 5 to 11 years of age, and in subjects ≥ 12 years of age.
- Computation of incidence rates of AFI due to LCD with 95% CI by type (DENV 1-4), study site and age group (6 months to 4 years, ≥ 5 years-11 years, ≥ 12 years to 17 years, ≥ 18 years): the numerator will be the number of subjects with AFI due to LCD in the category. The denominator will be the total person-years at risk in the category.

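### The design-effect formula in Protocol 9.2 uses a binomial reference variance for a person-time rate, so it does not estimate the design effect assumed in planning; the error for LCD is under 2%

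*Protocol*

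**What the plan says.** Protocol 9.2 deals with the design effect twice.

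- **Planning.** It takes D = 1 + (b - 1)ρ, where b is the number of subjects per household ("Here we assumed b to be 5") and ρ is set at 0.4 ("We used a conservative estimate of 0.4 for this study"). The result, 2.6, enters Table 17 through a Poisson variance: "The normal approximation of the Poisson distribution was used for calculating 95% CI for this cluster design", and "The variance was adjusted for a design effect of 2.6 to account for the between-cluster variability".
- **Analysis.** The design effect is to be estimated as a cluster-sample variance over a simple-random-sample variance, the latter being p(1-p)/n. The cluster quantities x_i and y_i "are the number of person-years and the number of cases, respectively"; p is Σy_i/Σx_i, although the text says that "p is the overall proportion"; and "n is the total number of person-years". The intra-cluster correlation then follows as (DE - 1)/[(Σx_i/c) - 1], with c the number of clusters.

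Protocol 9.6 confirms that the quantity of interest is a rate: "The denominator will be the total person-years at risk". SAP 9.2.1 defines it in the same way, on first events. SAP 9.2.2 gives exact Poisson limits, under a heading which says that clustering is not accounted for. The SAP has no design-effect calculation. SAP 8, which lists the omitted analyses, does not mention the design effect.

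**The concern.** A binomial variance p(1-p)/n describes n people, each scored 0 or 1. Person-years are not such trials. Their number depends on the unit of time, and p can exceed 1 if the unit is long enough. The same section therefore uses two reference variances: Poisson for the assumed 2.6 and binomial for the estimate to be set against it.

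What is at stake is the reported design effect itself, its comparison with 2.6, and any interval or intra-cluster correlation that someone later builds on it.

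**Working it through.** **1. The plan's own figures.** D = 1 + (5 - 1) × 0.4 = 2.6. With d cases in 3300 person-years, the limits are [d ± 1.96√(2.6d)]/33 per 100 person-years, with negative lower limits set to 0. At d = 60: √156 = 12.49, the half-width is 24.48 cases, and the limits are 1.08 and 2.56, as printed. All ten rows of Table 17 reproduce.

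A binomial variance multiplies the half-width by √(1-p) and misses four printed limits:

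| Cases | Limit | Printed | Poisson | Binomial |
|---|---|---|---|---|
| 12 | upper | 0.70 | 0.695 | 0.6948 (0.69) |
| 30 | lower | 0.38 | 0.3845 | 0.387 (0.39) |
| 40 | upper | 1.82 | 1.818 | 1.814 (1.81) |
| 60 | upper | 2.56 | 2.560 | 2.553 (2.55) |

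So Table 17 rests on p/n.

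**2. The two ratios.** The bracket in the cluster-sample variance, Σy_i² - 2pΣx_iy_i + p²Σx_i², equals Σ(y_i - p x_i)². The cluster-sample variance is therefore [c/(c-1)] Σ(y_i - p x_i)²/n².

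- Divided by p/n: DE = [c/(c-1)] Σ(y_i - p x_i)²/Σy_i. Each p x_i is an expected count, so the unit of time cancels.
- Divided by p(1-p)/n: the same quantity multiplied by 1/(1-p). Since p changes with the unit, so does the result.

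**3. Size for LCD, per person-year.**

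| Cases in 3300 | p | 1/(1-p) | True 2.6 reads |
|---|---|---|---|
| 10 | 0.00303 | 1.0030 | 2.608 |
| 20 | 0.00606 | 1.0061 | 2.616 |
| 40 | 0.01212 | 1.0123 | 2.632 |
| 60 | 0.01818 | 1.0185 | 2.648 |

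If the inflated value were used in an interval at 60 cases, the limits would be 1.070 and 2.567 instead of 1.076 and 2.560, a shift of about 0.007 per 100 person-years.

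**4. Size for a commoner event.** The documents give no non-LCD rate. At assumed rates of 10, 20 and 50 per 100 person-years, 1/(1-p) is 1/0.9 = 1.11, 1/0.8 = 1.25 and 1/0.5 = 2.00. At 20 per 100 person-years counted in months, p = 0.2/12 = 0.0167 and the factor falls to 1.017.

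**5. Check under the study's counting rule.** Person-time stops at the first event. Simulation used 400 households of 5 independent subjects, each followed for up to 1.65 years, with 2000 runs per rate, so the true design effect is 1.

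| Rate per 100 person-years | Printed formula | p/n form |
|---|---|---|
| 1.82 | 1.02 | 1.00 |
| 10 | 1.11 | 1.00 |
| 20 | 1.25 | 1.00 |
| 50 | 2.00 | 1.00 |

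**6. Intra-cluster correlation.** Planning divides DE - 1 by b - 1 = 4, and 1.6/4 = 0.40. The analysis formula divides by mean person-years per cluster minus 1. With 5 subjects × 3300/2000 = 1.65 years each, that is 8.25 - 1 = 7.25, and 1.6/7.25 = 0.22. The inflated 2.648 gives 1.648/7.25 = 0.23. In person-months the divisor is 99 - 1 = 98, and the result is 0.016.

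**The case against.** The strongest reply is that this has almost no practical effect. For LCD the excess is at most 1.9% over the planned range and would widen an interval. In a simulation with strong household heterogeneity (400 households of 5, about 46 cases, mean design effect about 2.25), the estimated design effect had a sampling standard deviation of about 0.33, against a formula bias of about 0.03. Protocol 9.6 does not say that the estimate enters any interval, and the SAP does not compute it. All of this stands and sets the weight of the point.

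A second reply is that counting only first events makes each subject a 0/1 outcome, so a binomial form may be right. This fails. The denominator is person-time cut off at the event, and step 5 shows that p/n recovers 1.00 under that rule while the printed form does not.

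A third reply is that the unit of time is not open: the protocol fixes person-years, and SAP 10.1.2.3 divides days by 365.25. That is correct. The unit dependence is a sign of a mis-specified formula, not a choice left to the analyst.

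**Conclusion.** The point holds as a formula mismatch of small size. The design effect that Protocol 9.2 promises at analysis is not the quantity assumed in planning; it is larger by exactly 1/(1-p). For LCD that means 0.3% to 1.9% over Table 17's overall range, on the conservative side. No LCD conclusion would change.

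Four stronger readings may tempt a reader, and the documents do not support them:

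- **That the study's confidence intervals are wrong for this reason.** The SAP's limits are exact Poisson limits and use no design effect.
- **That the error is large for non-LCD illness.** The 11%, 25% and 100% figures need both an assumed rate and use of the formula for that event. Section 9.2 discusses precision only for LCD and serotype-specific LCD.
- **That the intra-cluster correlation comes out too large.** With the person-year divisor it comes out well below the planning value, about 0.22 against 0.40, assuming 5 subjects and 1.65 years per subject. The binomial term moves it by less than 0.01.
- **That the error carries into Phase III planning.** Protocol 3.1 says that the study is to supply incidence data for sample-size calculation. It does not say that the design effect is carried forward.

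**What to change.** In Protocol 9.2, replace the simple-random-sample variance p(1-p)/n by p/n, and call p the overall rate. If a design effect is ever reported for non-LCD illness, use the same form.

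If the intra-cluster correlation is reported, replace the mean person-years per cluster in its divisor by the mean number of subjects per household, so that it matches b in the planning formula. Changing the variance alone would not repair this.

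The cost is one formula, one word and, where needed, one divisor. Data, design and conduct are unchanged. Since the SAP has no design-effect calculation to edit, the corrected form would go into the SAP only if that estimate is added; otherwise the study report can state it as a correction to the protocol formula.

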9.3. Cohorts for analyses

All the analyses of objectives and of demographics will be performed on the total cohort.

The Total cohort will include all subjects enrolled in the study.

9.4. Derived and transformed data

- An AFI case will be defined as:
 - LCD, if fever (body temperature $\geq 38^{\circ}\text{C}/\geq 100.4^{\circ}\text{F}$) on ≥ 2 consecutive calendar days *is measured at least twice*, at least 8 hours apart and if dengue RT-qPCR result on a blood sample taken during the 7-day period (Days 2-7) from the onset of fever is positive.
 - Non-LCD, if fever (body temperature $\geq 38^{\circ}\text{C}/\geq 100.4^{\circ}\text{F}$) on ≥ 2 consecutive calendar days is measured at least twice, at least 8 hours apart and if dengue RT-qPCR result on a blood sample taken during the 7-day period (Days 2-7) from the onset of fever is negative.
 - Undetermined, if fever (body temperature $\geq 38^{\circ}\text{C}/\geq 100.4^{\circ}\text{F}$) on ≥ 2 consecutive calendar days is measured at least twice, at least 8 hours apart but is not evaluated within the 7-day period (Days 2-7) from the onset

of fever and/or if dengue RT-qPCR result on a blood sample taken during the 7-day period (Days 2-7) from the onset of fever is invalid or missing.

- DENV-1 LCD, if fever (body temperature $\geq 38^{\circ}\text{C}/\geq 100.4^{\circ}\text{F}$) on ≥ 2 consecutive calendar days is measured at least twice, at least 8 hours apart in diary card and if positive result for DENV-1 by serotype-specific RT-qPCR on a blood sample taken within the 7-day period (Days 2-7) from the onset of fever is positive.
- DENV-2 LCD, if fever (body temperature $\geq 38^{\circ}\text{C}/\geq 100.4^{\circ}\text{F}$) on ≥ 2 consecutive calendar days is measured at least twice, at least 8 hours apart in diary card and if positive result for DENV-2 by serotype-specific RT-qPCR on a blood sample taken within the 7-day period (Days 2-7) from the onset of fever is positive.
- DENV-3 LCD, if fever (body temperature $\geq 38^{\circ}\text{C}/\geq 100.4^{\circ}\text{F}$) on ≥ 2 consecutive calendar days is measured at least twice, at least 8 hours apart in diary card and if positive result for DENV-3 by serotype-specific RT-qPCR on a blood sample taken within the 7-day period (Days 2-7) from the onset of fever is positive.
- DENV-4 LCD, if fever (body temperature $\geq 38^{\circ}\text{C}/\geq 100.4^{\circ}\text{F}$) on ≥ 2 consecutive calendar days is measured at least twice, at least 8 hours apart in diary card and if positive result for DENV-4 by serotype-specific RT-qPCR on a blood sample taken within the 7-day period (Days 2-7) from the onset of fever is positive.

- Age in the study will be computed as the difference between the date of enrolment (i.e., date of ICF [and IAF if applicable]) and the date of birth. The age will be expressed in years.
- The subject age at time of AFI will be computed as the difference between the date of the onset of fever (body temperature $\geq 38^{\circ}\text{C}/\geq 100.4^{\circ}\text{F}$) completed on diary card and the date of birth.
- The follow-up time for estimation of incidence of AFI due to LCD, will be computed, for each subject, as the difference between the date of first occurrence of AFI due to LCD (by serotype) or the date of last contact if no LCD occurred (i.e., last weekly Suspected Dengue Follow-up or last Visit) and the date of enrolment.
- The follow-up time for estimation of incidence of AFI due to non-LCD, will be computed, for each subject, as the difference between the date of first occurrence of AFI due to non-LCD or the date of last contact if any (i.e., last weekly Suspected Dengue Follow-up or last Visit) and the date of enrolment.
- The follow-up time for estimation of incidence of AFI due to LCD by DENV-1 type, will be computed, for each subject, as the difference between the date of first occurrence of AFI due to DENV-1 LCD or date of last contact if any (i.e., last weekly Suspected Dengue Follow-up or last Visit) and the date of enrolment. The same computations will be done for DENV-2-3 and 4 specific cases.

- The total person-years at risk will be computed as the sum of the follow-up times in year for each individual.
- The number of consecutive calendar days with fever (body temperature $\geq 38^{\circ}\text{C}/\geq 100.4^{\circ}\text{F}$) used for definition of cases will be computed as the number of consecutive calendar days with fever during the 7-day period following the onset of fever.
- The duration of symptoms will be computed as the number of days with grade 1, 2 or 3 symptoms during the 7 days following the onset of fever.
- For the analysis of solicited symptom, missing or non-evaluable measurements will not be replaced. Therefore the analysis of the solicited symptoms will include only episodes of AFI with documented safety data (i.e., diary card completed).
- The geometric mean titre (GMT) calculations are performed by taking the anti-log of the mean of the \log_{10} titre transformations. Antibody titres below the cut-off of the assay will be given an arbitrary value of half the cut-off for the purpose of GMT calculation. For a given subject and a given immunogenicity measurement, missing or non-evaluable measurements will not be replaced. Therefore, an analysis will exclude subjects with missing or non-evaluable measurements.

9.5. Analysis of demographics / baseline characteristics

Socio-demographic and patient characteristics (e.g., age at study enrolment, gender, household conditions, medical history and vaccination history) will be summarised overall and for LCD cases and by site using descriptive statistics.

9.6. Analysis of primary and secondary objectives

The following analyses will be performed:

- Computation of incidence rate of AFI due to LCD and due to non-LCD with 95% CI: the numerator will be the number of subjects with AFI due to LCD and due to non-LCD during the study period. The denominator will be the total person-years at risk.
- Description of signs and symptoms of AFI due to LCD and due to non-LCD will include the percentage of AFI presenting each sign or symptom (any intensity and grade 3) during the 7-day period from the onset of fever (body temperature $\geq 38^{\circ}\text{C}/\geq 100.4^{\circ}\text{F}$). Duration of signs and symptoms will also be described for LCD and non-LCD episodes. Analysis will be done overall and then separately for episodes of AFI occurring in subjects < 5 years of age, in subjects 5 to 11 years of age, and in subjects ≥ 12 years of age.
- Computation of incidence rates of AFI due to LCD with 95% CI by type (DENV 1-4), study site and age group (6 months to 4 years, ≥ 5 years-11 years, ≥ 12 years to 17 years, ≥ 18 years): the numerator will be the number of subjects with AFI due to LCD in the category. The denominator will be the total person-years at risk in the category.

9.7. Analysis of tertiary (research) objectives

Some tertiary (research) analyses may be done including:

(Amended 01 March 2017)

- Neutralising antibody titres against JEV: the seropositivity rates to JEV with exact 95% CI and GMTs with 95% CI and range of antibody titres will be tabulated.
- A concordance analysis between dengue virus detection by RT-qPCR and by NS1-antigen (***ICT test***) may be performed. This analysis may be stratified by day of sampling if sufficient data are available. Sensitivity, specificity, positive predictive value and negative predictive value of NS1-antigen (***ICT test***) in prediction of RT-qPCR test results will be computed. **(Amended 01 March 2017)**
- Computation of incidence rate of AFI due to dengue confirmed by NS1-antigen (ICT test and/or ELISA) with 95% CI: the numerator will be the number of subjects with AFI due to dengue confirmed by NS1-antigen (ICT test and/or ELISA) during the study period. The denominator will be the total person-years at risk.
- Evaluation of different case definitions by:
- Computation of incidence rates of AFI due to LCD having ≥ 3 consecutive calendar days of fever (body temperature $\geq 38^{\circ}\text{C}/\geq 100.4^{\circ}\text{F}$) or incidence of AFI due to LCD resulting in hospitalisation with 95% CI.
- Descriptive analysis of the signs and symptoms associated with AFI due to LCD having ≥ 3 consecutive calendar days of fever (body temperature $\geq 38^{\circ}\text{C}/\geq 100.4^{\circ}\text{F}$) or resulting in hospitalisation.
- Multivariate analyses could be done to identify categories of medically relevant signs and symptoms associated with high probability of LCD (any severity, having ≥ 3 consecutive calendar days of fever (body temperature $\geq 38^{\circ}\text{C}/\geq 100.4^{\circ}\text{F}$) and resulting in hospitalisation) *versus* non-LCD episodes using logistic regressions and/or classification and regression tree analysis to provide support for the definition of a moderate-to-severe dengue case for future clinical endpoint trials. Same analyses may be done to identify category of signs and symptoms associated with high probability of LCD having ≥ 3 consecutive calendar days of fever (body temperature $\geq 38^{\circ}\text{C}/\geq 100.4^{\circ}\text{F}$) or resulting to hospitalisation.
- Values of signs and symptoms in predicting LCD in AFI will be computed (sensitivity, specificity, positive predictive value and negative predictive value). Same computations may be done in predicting LCD having ≥ 3 consecutive calendar days of fever (body temperature $\geq 38^{\circ}\text{C}/\geq 100.4^{\circ}\text{F}$) or resulting to hospitalisation.
- Descriptive analysis of the spatio-temporal clustering of cases using a map of study households. Occurrence of AFI due to LCD within 2 weeks from an index case, in the same household or within 50 metres of the household of the index case will be analysed.
- Descriptive analysis of incidence and reason for hospitalisation in the study population, throughout the study period.

- Description of entomological characteristics such as vector species, vector density and breeding sites at selected site(s).

9.8. Analysis of SAEs related to study participation

The verbatim reports of SAEs related to study participation will be reviewed by a physician and the signs and symptoms will be coded according to the Medical Dictionary for Regulatory Activities (MedDRA). Every verbatim term will be matched with the appropriate PT. SAEs related to study participation reported during the entire study period will be described in individual data listings.

9.9. Interpretation of analyses

There are no confirmatory objectives with a pre-defined success criterion.

The exploratory (tertiary, research) analyses are not controlled for Type 1 error.

9.10. Conduct of analyses

Any deviation(s) or change(s) from the original statistical plan outlined in this protocol will be described and justified in the final study report.

9.10.1. Sequence of analyses

The final analysis will be performed when all prospective data have been collected and cleaned. A final study report containing data from the entire study will be written at this time.

(Amended 01 March 2017)

10. ADMINISTRATIVE MATTERS

To comply with ICH GCP or other applicable guidelines administrative obligations relating to data collection, monitoring, archiving data, audits, confidentiality, ownership and publications must be met.

10.1. Electronic Case Report Form instructions

A validated GSK defined electronic data collection tool will be used as the method for data collection.

In all cases, subject initials will not be collected nor transmitted to GSK. Subject data necessary for analysis and reporting will be entered/transmitted into a validated database or data system. Clinical data management will be performed in accordance with applicable GSK standards and data cleaning procedures.

While completed eCRFs are reviewed by a GSK Biologicals' Site Monitor at the study site, omissions or inconsistencies detected by subsequent eCRF review may necessitate clarification or correction of omissions or inconsistencies with documentation and approval by the investigator or appropriately qualified designee. In all cases, the investigator remains accountable for the study data.

Once the database is archived and the clinical study report is complete and approved by all parties, each participating investigator will be provided with a CD-ROM of the final version of the data generated at his/her investigational site.

